eCRF	electronic case report form
eC-SSRS	electronic Columbia-Suicide Severity Rating Scale
EAER	exposure adjusted event rate
EAIR	exposure adjusted incident rate

List of Abbreviations

EQ-5D-3L	European Quality of Life-5 Dimensions-3 Level questionnaire
ES	Enrolled Set
FAS	Full Analysis Set
FDA	Food and Drug Administration
geoCV	geometric coefficient of variation
GGT	gamma-glutamyltransferase
HiSCR	Hidradenitis Suppurativa Clinical Response
HiSQOL	Hidradenitis Suppurativa Quality of Life
HLT	high level term
HS	hidradenitis suppurativa
hs-CRP	high sensitivity C-reactive protein
HSSDD	Hidradenitis Suppurativa Symptom Daily Diary
HSSQ	Hidradenitis Suppurativa Symptom Questionnaire
IBD	Inflammatory bowel disease
IBD-CAC	Inflammatory Bowel Disease Adjudication Committee
ICF	Informed Consent Form
ICH	International Council for Harmonisation
IDC	Infectious Disease Committee
IGRA	interferon gamma release assay
IHS4	International Hidradenitis Suppurativa Severity Scoring System
IMP	investigational medicinal product
LFT	liver function tests
LLOQ	lower limit of quantification
LOCF	last observation carried forward
LSM	least square mean
MACE	major cardiovascular events
MAR	missing at random
MCID	minimal clinically important difference
MCMC	Markov-Chain Monte Carlo
MedDRA	Medical Dictionary for Regulatory Activities
MI	multiple imputation
MI-MCMC	multiple imputation Markov-Chain Monte Carlo

List of Abbreviations

MS	Maintenance Set
MSR	minimum significant ratio
n	number of study participants
NAb	neutralizing antibody
NI	Negative Immunodepletion
nR	New Ratio
NRI	nonresponder imputation
NRS	numeric rating scale
NS	Negative Screen
OC	observed case
PD	pharmacodynamic(s)
pDILI	potential drug induced liver injury
PEOT	premature end of treatment
PGI-C-HS	Patient Global Impression of Change in Hidradenitis Suppurativa Severity
PGI-C-SP	Patient Global Impression of Change in Severity of Skin Pain
PGI-S-HS	Patient Global Impression of Hidradenitis Suppurativa Severity
PGI-S-SP	Patient Global Impression of Severity of Skin Pain
PHQ-9	Patient Health Questionnaire 9
PI	Positive Immunodepletion
PK	pharmacokinetic(s)
PK-PPS	Pharmacokinetic Per-Protocol Set
PPS	Per-Protocol Set
PS	Positive Screen
PT	preferred term
████	████
████	████
QTcF	QT corrected for heart rate using Fridericia's formula
RS	Randomized Set
SAP	statistical analysis plan
SD	standard deviation
SE	standard error

List of Abbreviations

SFU	Safety Follow-up
SIB	suicidal ideation and behavior
SMQ	standardized MedDRA query
SOC	system organ class
SS	Safety Set
SSD	Safety Signal Detection
TEAE	treatment-emergent adverse event
TEMA	treatment-emergent markedly abnormal
TSQM-9	Treatment Satisfaction Questionnaire – Medication 9
ULN	upper limit of normal
VAS	visual analogue scale
WHODD	World Health Organization Drug Dictionary
WPAI-SHP	Work Productivity and Activity Impairment Questionnaire-Specific Health Problem

This document cannot be used to support any marketing authorization application and any extensions or variations thereof.

1 INTRODUCTION

This statistical analysis plan (SAP) defines the scope of statistical analyses and provides a detailed description of statistical methodology to support the final clinical study report (CSR).

The SAP is based on the Protocol Amendment 4, 6 May 2022 and the Japan-specific amendment 4.1, 16 June 2022. If a future protocol amendment necessitates a substantial change to the statistical analysis of the study data, this SAP may be amended accordingly. The content of this SAP is compatible with the International Council for Harmonisation (ICH)/Food and Drug Administration (FDA) E9 Guidance documents.

2 PROTOCOL SUMMARY

2.1 Study objectives

2.1.1 Primary objective

The primary objective of this study is to evaluate the efficacy of bimekizumab in study participants with moderate to severe hidradenitis suppurativa (HS).

2.1.2 Secondary objectives

The secondary objectives of this study are to:

- Evaluate the efficacy of bimekizumab on other measures of disease activity in study participants with moderate to severe HS
- Evaluate the safety of bimekizumab in study participants with moderate to severe HS

2.1.3 Other objectives

The other objectives of this study are to:

- Evaluate the efficacy of bimekizumab on Hidradenitis Suppurativa Clinical Response (HiSCR), other HS Scores, and other clinical measures of disease activity at various timepoints in study participants with moderate to severe HS
- Evaluate the efficacy of bimekizumab on abscesses, nodules, and draining tunnels at various timepoints in study participants with moderate to severe HS
- Evaluate the efficacy of bimekizumab on patient-reported outcome measures at various timepoints in study participants with moderate to severe HS
- Evaluate the effect of bimekizumab on other safety measures at various timepoints in study participants with moderate to severe HS
- Evaluate the pharmacokinetics (PK) of bimekizumab in study participants with moderate to severe HS
- Evaluate the immunogenicity of bimekizumab (antidrug antibodies) in study participants with moderate to severe HS

2.1.4 Exploratory objective

The exploratory objective of the study is to evaluate biomarkers in study participants with moderate to severe HS.

2.2 Study endpoints

2.2.1 Efficacy endpoints

2.2.1.1 Primary efficacy endpoint

The primary efficacy endpoint is the HiSCR₅₀ (defined as at least a 50% reduction from Baseline in the total abscess and inflammatory nodule [AN] count with no increase from Baseline in abscess or draining tunnel count) at Week 16.

2.2.1.2 Secondary efficacy endpoints

The secondary efficacy endpoints are defined as:

- HiSCR₇₅ response (defined as at least a 75% reduction from Baseline in the total AN count with no increase from Baseline in abscess or draining tunnel count) at Week 16
- Flare (defined as a $\geq 25\%$ increase in AN count with an absolute increase in AN count of ≥ 2 relative to Baseline) by Week 16
- Absolute change from Baseline in Dermatology Life Quality Index (DLQI) Total Score at Week 16
- Absolute change from Baseline (CFB) in Skin Pain score at Week 16, as assessed by the “worst skin pain” item (11-point numeric rating scale) in the HS Symptom Daily Diary (HSSDD)
- Skin pain response based on the threshold for clinically meaningful change (defined as at least a 3 point decrease from Baseline in HSSDD weekly worst skin pain score) at Week 16 among study participants with a score of ≥ 3 at Baseline

2.2.1.3 Other efficacy endpoints

The other efficacy endpoints are defined as:

- Time to response of HiSCR₂₅, HiSCR₅₀, HiSCR₇₅, HiSCR₉₀, and HiSCR₁₀₀
- HiSCR₂₅, HiSCR₅₀, HiSCR₇₅, HiSCR₉₀, and HiSCR₁₀₀
- Absolute change from Baseline in International Hidradenitis Suppurativa Severity Score System (IHS4)
- Change from Baseline in the HS-Physician’s Global Assessment 6-point scale
- Absolute and percentage change from Baseline in high-sensitivity C-reactive protein (hs-CRP)
- Initiation of systemic antibiotic rescue therapy
- HiSCR₂₅, HiSCR₅₀, HiSCR₇₅, HiSCR₉₀, and HiSCR₁₀₀ at both Weeks 16 and 48
- Time to loss of response of HiSCR₅₀, HiSCR₇₅, HiSCR₉₀, and HiSCR₁₀₀ in Week 16 responders
- Partial responders (defined as a $\geq 25\%$ reduction in AN count from Baseline [Week 0]) at Week 16 who progress to HiSCR₅₀ during the Maintenance Treatment Period

- Partial responders (defined as a $\geq 25\%$ reduction in AN count from Baseline [Week 0]) at Week 16 who progress to HiSCR₇₅, HiSCR₉₀, and HiSCR₁₀₀ response during the Maintenance Treatment Period
- Change and percentage change from Baseline in lesion counts (abscess count, inflammatory nodule count, AN count, and draining tunnel count)
- AN count of 0, 1, or 2
- AN₂₅, AN₅₀, AN₇₅, AN₉₀, AN₁₀₀ (defined as a 25%, 50%, 75%, 90%, 100% reduction in the total AN count relative to Baseline)
- Flare (defined as a $\geq 25\%$ increase in AN count with an absolute increase in AN count of ≥ 2 relative to Week 16) by Week 48
- Time to flare from Weeks 0 to 16
- Time to flare from Week 16 to 48
- Absolute and percentage change (worst and average skin pain) from Baseline in HS Skin Pain score (11-point numeric rating scale)
- Skin pain response based on the threshold for clinically meaningful change (defined as at least a 3 point decrease from Baseline in HSSDD weekly worst skin pain score) among study participants with a score of ≥ 3 at Baseline
- Skin pain response (at least a 30% reduction and at least a 1-point reduction from Baseline in HSSDD weekly worst skin pain score [11-point numeric rating scale]) among study participants with a score of ≥ 3 at Baseline
- Skin pain response (at least a 30% reduction and at least a 1-point reduction from Baseline in HSSDD weekly average skin pain score [11-point numeric rating scale]) among study participants with a score of ≥ 3 at Baseline
- Skin pain response (at least a 30% reduction and at least a 1-point reduction from Baseline in HS Skin Pain score [11-point numeric rating scale]) assessed by the HSSQ among study participants with a score of ≥ 3 at Baseline
- Absolute change from Baseline in DLQI Total Score
- DLQI Total Score of 0 or 1
- Minimum clinically important difference (MCID) (improvement from Baseline of 4 or more) in the DLQI Total Score among study participants with a Baseline score of at least 4
- Absolute change from Baseline in Hidradenitis Suppurativa Quality of Life (HiSQOL) domain scores (symptoms, psychosocial, activities and adaptations) and Total score
- Patient Global Impression of HS Severity (PGI-S-HS)
- Patient Global Impression of Change of HS Severity (PGI-C-HS)
- Patient Global Impression of Severity of Skin Pain (PGI-S-SP)
- Patient Global Impression of Change of Skin Pain (PGI-C-SP)

- Absolute change from Baseline in each of the other HS Symptoms - itch, drainage or oozing of HS lesions, and smell or odor
- Response on other HS Symptoms (11-point numeric rating scale) - itch, drainage or oozing of HS lesions, and smell or odor
- Responses to the European Quality of Life-5 Dimensions-3 Level questionnaire (EQ-5D-3L), absolute and changes from Baseline in EQ-5D-3L visual analog scale (VAS) scores
- Absolute change from Baseline in Work Productivity and Activity Impairment Questionnaire-Specific Health Problem (WPAI-SHP) v2.0 adapted to HS scores
- Domain Scores (effectiveness, convenience and global satisfaction) on the Treatment Satisfaction Questionnaire – Medication-9 (TSQM-9)

2.2.2 Pharmacokinetic and pharmacogenomic endpoints

2.2.2.1 Pharmacokinetic endpoints

The PK endpoint is the plasma bimekizumab concentrations over the study duration.

2.2.2.2 Exploratory pharmacogenomic endpoints

Genomic, genetic, epigenetic, proteins, and metabolite biomarkers may be measured to evaluate the relationship with response to treatment with bimekizumab, HS disease biology, and inflammatory and immune response processes. The candidate exploratory biomarkers are the blood or blood derivative (eg, plasma) concentrations of cytokines and chemokines of relevance to the IL-17A/F signaling pathway and HS biology.

Additional biomarkers may include, but will not be limited to, plasma complement concentrations.

A specific SAP will be written to describe the analysis methods for those endpoints, as the results will not be summarized in the CSR. The nature and format of these analyses will be detailed in this SAP.

2.2.3 Safety endpoints

2.2.3.1 Secondary safety endpoints

The secondary safety endpoints are

- Treatment-emergent Adverse Events (TEAEs)
- Serious TEAEs
- TEAEs leading to withdrawal from study

2.2.3.2 Other safety endpoints

The other safety endpoints are

- Adverse events of special interest (Hy's Law)
- Other safety topics of interest: infections (serious, opportunistic, fungal, and TB), neutropenia, hypersensitivity (including anaphylaxis), suicidal ideation and behavior, major adverse cardiovascular events, hepatic events and potential drug-induced liver injury (PDILI), malignancies, and inflammatory bowel disease.

- Absolute change from Baseline in the Patient Health Questionnaire (PHQ-9) score
- Absolute change from Baseline in vital signs
- Absolute change from Baseline in clinical laboratory values (chemistry and hematology)
- Electrocardiogram (ECG) results

2.2.4 Immunological endpoints

The immunological endpoints are

- Bimekizumab antidrug antibodies
- Bimekizumab neutralizing antibodies

The results of the bimekizumab neutralizing antibody analysis will not be summarized in the CSR for this study. All neutralizing antibody analyses will be detailed in the integrated immunogenicity SAP.

[figure not shown]
2.3 Study design and conduct

2.3.1 Study description

HS0004 is a Phase 3, randomized, double-blind, placebo-controlled, multicenter, pivotal study evaluating the efficacy and safety of bimekizumab in study participants with moderate to severe HS. Study participants meeting the inclusion criteria who do not meet any exclusion criteria will complete a Screening Period of 14 days to up to 5 weeks; a double-blind, 48-week Treatment Period comprising a 16-week Initial Treatment Period and 32-week Maintenance Treatment Period; and a 20-week Safety Follow-up (SFU) Period following the final injection of investigational medicinal product (IMP) if study participants do not enter a subsequent extension study (HS0005) or withdraw prematurely from treatment.

Study participants will be randomized in a 2:2:2:1 ratio (stratified by Hurley Stage and current antibiotic use) to 1 of 3 dose regimens of bimekizumab or placebo as shown in the schematic (Figure 2-1).

Figure 2-1: Study Schematic

HiSCR₅₀=a 50% reduction in the total abscess and inflammatory nodule count with no increase from Baseline in abscess or draining tunnel count;

IMP=investigational medicinal product; [REDACTED]

*Week 16 = primary endpoint (HiSCR₅₀ bimekizumab versus placebo)

a Study participant should discontinue from the study from Week 32 on if no partial response is achieved (partial response is defined as $\geq 25\%$ improvement in abscess and inflammatory nodule count relative to Baseline [Week 0] lesion values.)

b Study participants achieving an improvement of at least 25 % in abscess and inflammatory nodule count continue in HS0005 (Extension Study).

c 20-week Safety Follow-up (from last IMP injection) for any study participant who discontinues from study prior to Week 48, or who does not continue in HS0005.

2.3.2 Study periods

2.3.2.1 Screening Period

The Screening Period will last a minimum of 14 days up to a maximum of 5 weeks prior to randomization.

2.3.2.2 Initial Treatment Period (Weeks 0-16) and Maintenance Treatment Period (Weeks 16-48)

Eligible study participants will be randomized in a 2:2:2:1 ratio as noted in the Study Schema to:

- Bimekizumab [REDACTED] from Weeks 0 to 48
- Bimekizumab [REDACTED] from Weeks 0 to 48
- Bimekizumab [REDACTED] to Week 16, continuing on [REDACTED] from Weeks 16 to 48
- Placebo to Week 16, continuing on bimekizumab [REDACTED] from Weeks 16 to 48

2.3.2.3 Safety Follow-up Visit

All study participants not continuing in the extension study, including those withdrawn from IMP as well as those completing all study visits, will have an SFU Visit 20 weeks after their final dose of IMP.

2.3.3 Study duration per participant

The total duration of study participation in HS0004 will be 68 to 71 weeks for those who complete HS0004 and do not participate in the extension study HS0005 and 50 to 53 weeks for those who participate in HS0005 and, thus, do not participate in the 20-week SFU Period. The study is comprised of the following periods:

- Screening Period: 14 days up to a maximum of 5 weeks prior to randomization
- Initial Treatment Period: 16 weeks
- Maintenance Treatment Period: 32 weeks
- Safety Follow-Up Period: 20 weeks after the last dose of IMP

A study participant will be considered to have completed the study if he or she completed the Week 48 visit.

The end of the study is defined as the date of the last scheduled procedure for the last study participant in the study globally, including the SFU, as applicable.

2.3.4 Planned number of participants and sites

A total of approximately 490 study participants will be randomized into the study. The planned number of study sites is approximately 100.

2.3.5 Anticipated regions and countries

The regions planned for study conduct are Western Europe, Central/Eastern Europe, North America and Asia/Australia, with possible extension to other regions and countries.

A subset of tables, listings, and figures will be repeated for the subgroup of participants randomized in Japan. A list of these outputs will be added to the tables, figures, and listings shells.

2.4 Determination of sample size

A total of 490 study participants will be randomly assigned in a 2:2:2:1 ratio (stratified by Hurley Stage and current antibiotic use) to the following treatment arms:

- Bimekizumab ██████████ during Initial Treatment Period (Weeks 0-16) and Maintenance Treatment (Weeks 16-48) Period, N=140
- Bimekizumab ██████████ during Initial Treatment Period (Weeks 0-16), and Bimekizumab ██████████ during Maintenance Treatment Period (Weeks 16-48), N=140
- Bimekizumab ██████████ during Initial Treatment (Weeks 0-16) and Maintenance Treatment Periods (Weeks 16-48), N=140
- Placebo during Initial Treatment Period (Weeks 0-16), and Bimekizumab ██████████ during Maintenance Treatment Period (Weeks 16-48), N=70

The analysis of the primary efficacy endpoint and secondary efficacy endpoints are based on a comparison of bimekizumab versus placebo at Week 16, with alpha adjustment strategy as indicated in Section 4.5.

The power to detect a statistically significant difference for each of the endpoints are shown in Table 2-1. Notably, with a 2-sided significance level of 0.025, the sample size of 140:70 provides 73% power for detecting at least a difference of 1.5 (bimekizumab ██████████ vs placebo) for the Worst Skin Pain change from Baseline (CFB) endpoint.

Given the high level of power for each of the primary and key secondary endpoints at the 0.025 significance level for the ██████████ comparison (power \geq 0.89), and per the alpha spending strategy, there is a high likelihood that the ██████████ comparison of Worst Skin Pain CFB vs placebo will be allowed to be tested against the 0.05 level of significance. The power for this latter test is 81%. The sample size is thus ultimately driven by the Worst Skin Pain CFB endpoint.

Furthermore, the randomization ratio of 2:2:2:1 has been chosen to provide study participants with a high probability (6/7 ~ 86%) of being randomized to active study drug.

After randomization for this study was complete, an additional endpoint to assess Worst Skin Pain response was included in the sequential testing procedure. This additional endpoint is based on the threshold for clinically meaningful change and is defined as at least a 3 point decrease from Baseline in HSSDD weekly worst skin pain score at Week 16 among study participants with a score of \geq 3 at Baseline. Note that the power calculations reported in Table 2-1 for this

endpoint are based on the sample size that was initially driven by the Worst Pain CFB endpoint as described above. With a 2-sided significance level of 0.025, the sample size of 104:52 in the subset of participants reporting Baseline HSSDD worst skin pain score at or beyond the threshold for clinically meaningful change (ie, Baseline HSSDD ≥ 3) provides 53% power for detecting a statistically significant difference between bimekizumab [REDACTED] and placebo in the proportion of Worst Pain responders.

Note that the power at the 0.025 level of significance associated with this endpoint for the comparison between bimekizumab [REDACTED] and placebo is 95%. The [REDACTED] comparison of Worst Skin Pain response vs placebo against the 0.05 level of significance is therefore likely, and the power at this significance level is 65%. Given the strength of the power for the bimekizumab [REDACTED] arm vs placebo across endpoints, it is considered acceptable to have a relatively low power for this final endpoint in the testing sequence for the bimekizumab [REDACTED] treatment arm vs placebo.

Table 2–1: Power calculation assumptions and methods

Endpoint	Power $\alpha = 0.025$, 2-sided		Assumptions		
	[REDACTED]	[REDACTED]	Week 16 Bimekizumab [REDACTED] N=280 ^a	Week 16 Bimekizumab [REDACTED] N=140	Week 16 Placebo N=70
HiSCR ₅₀	0.99	0.90	Proportion responders=0.60	Proportion responders=0.50	Proportion responders=0.25
HiSCR ₇₅	0.99	0.98	Proportion responders=0.45	Proportion responders=0.35	Proportion responders=0.10
Flare	0.99	0.99	Proportion of participants with flare by Week 16=0.09	Proportion of participants with flare by Week 16=0.19	Proportion of participants with flare by Week 16=0.52
DLQI	0.99	0.96	Mean CFB=-5.4; SD=6.8	Mean CFB=-4.8; SD=6.8	Mean CFB=-0.8; SD=6.6
Worst Skin Pain CFB ^b	0.89	0.73	Mean CFB=-2.2; SD=3.2	Mean CFB=-2.0; SD=3.2	Mean CFB=-0.5; SD=3.7
Worst Skin Pain Response ^c	0.95	0.53	Proportion responders=0.53	Proportion responders=0.43	Proportion responders=0.23

CFB=change from Baseline; [REDACTED] SD=standard deviation

Note: Estimates for HS0004 are based on Week 12 data from the HS0001 study.

^a Pooled [REDACTED] at Week 16 from [REDACTED] and [REDACTED] arms

^b Within-participant average of Worst Skin Pain according to 24-hour recall.

^c Assumes N=208, 104, 52 in [REDACTED] and placebo, respectively, to account for Worst Skin Pain score at or above 3 (ie, the threshold for clinically meaningful change from Baseline)

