4.5 Multiple comparisons/multiplicity

To control the overall type I error rate at 0.05 for the multiple comparisons in the primary and secondary efficacy endpoints, a closed testing procedure under a parallel gatekeeping framework will be applied (Sun, 2018).

[figure not shown]
Under this framework, each bimekizumab dose of [REDACTED] and [REDACTED] will be compared to placebo in the first instance at a familywise error rate of 0.025 ($\alpha/2$). Simultaneously within each dose, closed testing for the primary and secondary efficacy endpoints will be performed as follows:

1. Step 1: Test HiSCR₅₀ at significance level 0.025.
2. Steps 2 to 6 – If Step 1 is significant at 0.025 then test each secondary endpoint sequentially in the order shown in Figure 4-1, moving to the next step only if significance achieved at 0.025.
3. In the event that Step 6 is significant at 0.025 for a given dose, then Steps 1 to 6 will be repeated for the other dose using a significance level of 0.05.

The secondary efficacy variables supporting the primary efficacy variable are listed below, and will be included in the multiplicity adjustment using the analysis methods specified in Section 8.3:

1. Proportion of study participants who achieve HiSCR₇₅ at Week 16.
 - a. bimekizumab [REDACTED] vs placebo
 - b. bimekizumab [REDACTED] vs placebo
2. Proportion of study participants who experience at least 1 flare by Week 16, with flare defined as a $\geq 25\%$ increase in AN count with an absolute increase in AN count of ≥ 2 relative to Baseline.
 - a. bimekizumab [REDACTED] vs placebo
 - b. bimekizumab [REDACTED] vs placebo
3. Absolute CFB in DLQI Total Score at Week 16.
 - a. bimekizumab [REDACTED] vs placebo
 - b. bimekizumab [REDACTED] vs placebo
4. Absolute CFB in Skin Pain Score at Week 16, as assessed by the “worst skin pain” item (11-point numeric rating scale) in the HSSDD.
 - a. bimekizumab [REDACTED] vs placebo
 - b. bimekizumab [REDACTED] vs placebo
5. Skin pain response at Week 16, based on the threshold for clinically meaningful change (defined as at least a 3 point decrease from Baseline in HSSDD weekly worst skin pain score) at Week 16 among study participants with a score of ≥ 3 at Baseline.
 - a. bimekizumab [REDACTED] vs placebo
 - b. bimekizumab [REDACTED] vs placebo

Figure 4-1: Sequence of testing

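### Section 2.4 sizes the trial on single-test powers; under the gated Section 4.5 rule the sizing endpoint has about 71–80% power, against 81% for the isolated test

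*SAP*

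**What the plan says.** SAP Section 2.4 and Table 2-1 give, for each endpoint, the power of a comparison with placebo at 2-sided 0.025. The regimen names are redacted, so I call the regimens N=280 (two arms pooled to Week 16) and N=140; placebo has 70.

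- For Worst Skin Pain CFB in the N=140 regimen: "with a 2-sided significance level of 0.025, the sample size of 140:70 provides 73% power for detecting at least a difference of 1.5".
- Because every primary and key secondary endpoint of the N=280 regimen has power of at least 0.89, Section 2.4 says "there is a high likelihood that the" N=140 pain comparison will be tested at 0.05. It then concludes: "The power for this latter test is 81%. The sample size is thus ultimately driven by the Worst Skin Pain CFB endpoint".
- For the pain response endpoint, added after randomization was complete, it gives 95% for N=280 at 0.025. From this it infers that the N=140 test at 0.05 "is therefore likely, and the power at this significance level is 65"%.

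Section 4.5 sets the rule. Within a regimen, the six steps (HiSCR50, HiSCR75, flare, DLQI, pain CFB, pain response) are tested in order and testing stops at the first failure. The higher level becomes available as follows: "In the event that Step 6 is significant at 0.025 for a given dose, then Steps 1 to 6 will be repeated". This second pass concerns the regimen that has not yet cleared the sequence, and it uses the 0.05 level.

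**The concern.** Section 2.4 relies on the Section 4.5 alpha recycling to move from 73% to 81%, but it does not count what the recycling requires. Two sets of events must occur before N=140 pain CFB can be declared at 0.05:

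1. The N=280 regimen is significant at 0.025 on all six steps. Section 2.4 covers this only in words.
2. The N=140 regimen passes its own four upstream tests. The sizing argument does not mention this, although Table 2-1 gives only 0.90 for HiSCR50 and 0.96 for DLQI in that regimen at 0.025.

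A gated claim cannot be more probable than its ungated test, so the direction of the discrepancy is certain. At stake is whether the power used to justify the trial's size is one that its decision rule delivers.

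**Working it through.** **Inputs.** From Section 2.4 and Table 2-1: "A total of 490 study participants will be randomly assigned in a 2:2:2:1 ratio"; pain CFB "Mean CFB=-2.2; SD=3.2" (N=280), "Mean CFB=-2.0; SD=3.2" (N=140), and mean −0.5, SD 3.7 (placebo, N=70); pain response 0.53, 0.43 and 0.23 in 208, 104 and 52 participants. From Section 4.5: the stop-at-first-failure order and the release condition.

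**Step 1. Reproduce the printed powers as single tests.** For N=140 pain CFB:

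- SE = √(3.2²/140 + 3.7²/70) = √(0.0731 + 0.1956) = 0.518; 1.5/0.518 = 2.89.
- Unequal-variance t-test: 0.733 at 0.025 (printed 0.73) and 0.819 at 0.05 (printed 81%).

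For N=280 pain CFB at 0.025 the same method gives 0.893 (printed 0.89). For pain response, a continuity-corrected chi-square gives 0.952 (printed 0.95), 0.526 (0.53) and, at 0.05, 0.641 (65%). All three disputed figures are therefore single-test powers, correct to within about a point. Without the continuity correction the response powers are 0.97, 0.59 and 0.70. The simulation below takes its effect sizes from the printed powers, so that a change of test is not mixed with the effect of gating.

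**Step 2. A bound that needs no correlation.** The N=280 regimen releases 0.05 only if it passes Step 6 at 0.025, hence also Step 5 at 0.025, whose power is 0.89. So P(release) ≤ 0.89, and the 95% cannot stand for it. The power of N=280 pain response under the rule is held to about the same ceiling. It can exceed it only through the rare route in which the N=140 regimen passes all six steps first and N=280 is re-tested at 0.05.

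**Step 3. Cost of the N=140 upstream gates, by hand under independence.** Standardised effect = z(power at 0.025) + 2.241; power at 0.05 = Φ(effect − 1.960).

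| N=140 gate | Power at 0.025 (Table 2-1) | Effect | Power at 0.05 |
|---|---|---|---|
| HiSCR50 | 0.90 | 3.523 | 0.941 |
| HiSCR75 | 0.98 | 4.295 | 0.990 |
| Flare | 0.99 | 4.568 | 0.995 |
| DLQI | 0.96 | 3.992 | 0.979 |

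The product is 0.908. With the release condition applied but the gates ignored, pain CFB power is about 0.80 (Step 4), and 0.908 × 0.80 ≈ 0.73. This is slightly above the simulated 0.71–0.72 because some declarations come by the 0.025 route, where the gates are harder to pass.

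**Step 4. The full rule.** Simulation of 12 jointly normal test statistics (1,000,000 draws), with between-dose correlation √(280/350 × 140/210) = 0.73 from the shared placebo arm. Between-endpoint correlation is an assumption. The N=280 regimen's first four endpoints are set at the printed 0.99.

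| Endpoint correlation (pain CFB with pain response) | N=140 pain CFB | Same, N=140 gates ignored | P(N=280 releases 0.05) | N=280 pain response | N=140 pain response |
|---|---|---|---|---|---|
| 0 (0) | 0.714 | 0.794 | 0.811 | 0.821 | 0.456 |
| 0.3 (0.6) | 0.740 | 0.795 | 0.842 | 0.851 | 0.548 |
| 0.5 (0.7) | 0.760 | 0.796 | 0.857 | 0.864 | 0.577 |
| 0.7 (0.8) | 0.781 | 0.799 | 0.871 | 0.878 | 0.603 |
| 0.9 (0.9) | 0.797 | 0.800 | 0.884 | 0.890 | 0.623 |
| Printed (single test) | 0.81 | – | not given | 0.95 | 0.65 |

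Setting those four endpoints near 1, as recomputation suggests, moves N=140 pain CFB to 0.721 at correlation 0 and leaves it at 0.797 at 0.9.

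**Step 5. Where the loss arises.** The release condition alone lowers pain CFB from 0.81 to 0.79–0.80. The N=140 regimen's own gates account for the rest, mainly HiSCR50. Releasing after Step 5 instead of Step 6 would change pain CFB power by at most 0.6 points.

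**The case against.** The strongest defence is that nothing is miscalculated. Section 2.4 describes 81% as the power of one test once that test is allowed, prints the fallback of 73%, and cross-refers to Section 4.5. It also openly accepts low power for the last endpoint in the N=140 regimen. A release probability of 0.81–0.89 can fairly be called likely. All of that stands.

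Four stronger readings are tempting and are not supported:

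- *That 81%, 95% and 65% are arithmetic errors.* They reproduce as single-test powers and are worded as such.
- *That one narrow figure should replace 81%.* The result depends on a correlation the SAP does not give. At 0.9 the gap for pain CFB is only one to two points.
- *That the endpoint added after randomization caused the loss.* Step 5 of the working shows that it costs pain CFB little.
- *That the trial must be larger or the order changed.* Type I error, the estimates, and the Step 1 HiSCR50 powers (0.99 and 0.90) are unaffected.

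What the defence does not answer is that the sizing sentence rests on the 81%, while the stated condition covers only the N=280 regimen and omits the N=140 regimen's own gates, which cause most of the loss.

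**Conclusion.** The point holds as a fault in the sample size justification: single-test powers support claims that are made under a gated rule. Over an assumed between-endpoint correlation of 0 to 0.9, N=140 pain CFB has about 71–80% power, against 81% for the single test. The gap exceeds two points for correlations up to about 0.7. N=280 pain response has about 82–89% (printed 95%) and N=140 pain response about 46–62% (printed 65%). The 0.05 level is released with probability about 0.81–0.89; the ceiling of 0.89 holds whatever the correlation. The other figures rest on the Table 2-1 effects being true, on jointly normal test statistics, and on the assumed correlation.

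**What to change.** In Section 2.4 and Table 2-1:

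- Keep the printed figures and label them as single-test powers.
- Add the power of each step for each regimen under the Section 4.5 rule, stating the correlation assumed or a range.
- Base the sizing statement for Worst Skin Pain CFB on the power under the rule (about 71–80%).
- Replace the two verbal statements of likelihood with the computed release probability (about 0.81–0.89).

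The cost is one simulation and some wording. The stated power becomes less favourable; sample size, testing order and analysis stay as they are.
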